## ABBREVIATIONS

CD	Crohn's Disease
CDAI	Crohn's Disease Activity Index
CDI	Clostridioides difficile infection
DSMC	Data Safety Monitoring Committee
FMT	Fecal Microbiota Transplantation
IBD	Inflammatory Bowel Disease
IBS	Irritable Bowel Syndrome
IBS-SSS	Irritable Bowel Syndrome Severity Scoring System
LYO-FMT	Lyophilized Fecal Microbiota Transplant
MC	Microscopic Colitis
PROM	Patient Reported Outcome Measure
UC	Ulcerative Colitis

## Study Rationale and Background

Fecal Microbiota Transplantation (FMT), which had been predominantly utilized by the veterinarians until late 1990's has generated a significant interest for its potential use in various gastrointestinal, psychiatric, neurologic and metabolic disorders within the past few years. Since 2010, there has been an explosion of research, publications and media coverage related to the high efficacy range, 80 – 90% for treatment of recurrent *Clostridioides (Clostridium) difficile* infection (rCDI). The exact mechanisms of its success in curing CDI are yet to be discovered. However, growing evidence suggests that it likely is a synergistic interaction of metabolites, bacteriophages, glycoproteins and bacterial, fungal components of microbiome, which mediate the effects of FMT. Metagenomic studies have shown that patients with rCDI lack protective and diverse colonic microbiome and remain in a state of chronic dysbiosis. Following a successful FMT, the microbiome of a patient with rCDI resembles that of the donor's and remains as such overtime. There is no precise and agreed definition of dysbiosis. For the purpose of this study, dysbiosis is defined as perturbation of host-microbial interactions which results in compositional changes in the fecal microbiota as determined by clinical criteria of constellation of symptoms, including change in the bowel function (diarrhea, constipation or bloating) in which an alteration of the microbiota is either known based on molecular or culture-based profiling or suspected according to the history, which includes but is not limited to repeated or prolonged use of antibiotics or gastrointestinal infection.

The cause of inflammatory bowel disease (IBD) is unknown but studies have shown that IBD is a chronic inflammatory disease with altered and decreased microbiota diversity of the gastrointestinal tract when compared to the healthy individuals. Canada has the highest incidence of IBD in the world. The annual total (direct and indirect) health costs is estimated to \$2.8 billion or \$11,900 per person per year. IBD includes Crohn's Disease (CD) and Ulcerative Colitis (UC). While these diseases are collectively referred as IBD, there are distinct differences - most notably the area of the intestinal tract affected and the extent of the inflammation. UC typically affects the colon; the disease usually starts at the anus and may progress upward, and may even involve the entire colon. While in CD, the inflammation tends to occur in patches and may involve any area throughout the entire intestinal tract; however, it most often affects the terminal ileum of the small intestine. Inflammation due to UC involves only the inner intestinal mucosa, while the inflammation in CD disease can extend through the entire thickness of the bowel wall.

The management of CD is challenging due to extra-intestinal manifestations and overlapping symptomology with other inflammatory disorders. Treatment typically targets symptom relief, but patients' ability to tolerate therapy also plays a key role. UC is characterized by lifelong relapsing and remitting colorectal inflammation. The cause of UC is unknown, but is thought to result from an aberrant immune response to environmental factors in genetically predisposed individuals. Metagenomic studies have shown that both patients with UC and recurrent *Clostridioides difficile* infection (rCDI) lack diversity and richness of their colonic microbiota and remain in a state of chronic dysbiosis. While current drug treatments and surgery to remove the colon and rectum can reduce symptoms, they are costly, associated with adverse effects, and do not promote the restoration of healthy gut bacteria. Recent studies have shown that fecal microbiota transplant (FMT) is effective in treating IBD. Recent case series in CD and clinical trials in UC patients have shown FMT to be a potential therapy to induce and maintain clinical remission in subset of IBD patients.

Microscopic colitis (MC) is a chronic inflammatory disease of the colon as manifested by chronic, watery, non-bloody diarrhea. MC usually occurs in middle-aged individuals with a female preponderance. Currently, there are limited treatment options for MC; budesonide may be effective for short-term treatment of MC and can improve quality of life. However, up to 80% will experience symptomatic relapse following cessation of budesonide. Routine maintenance treatment with budesonide is controversial as long-term treatment may increase the risk of steroid-related side effects.

IBS is characterized by chronic, relapsing abdominal discomfort and altered bowel movements – constipation, diarrhea or mixed (diarrhea and constipation). IBS affects approximately 15-20% of Canadians and its economic and social burden is estimated to be over \$6.5 billion per year in healthcare costs, work productivity losses, and reduced quality of life (QoL). The etiology and pathophysiology of IBS are not yet established, but appear to be a complex interplay between the host and environment factors. Currently, there are no evidence-based therapies available to cure IBS. Studies have shown that fecal microbiota transplantation (FMT) may be an effective IBS treatment. Given the lack of safe and effective treatment for IBD and IBS which are thought to be due to gastronintestinal dysbiosis, this study was conducted.

There is also some evidence in the literature showing efficacy of FMT in clearance of antimicrobial resistant organism (ARO) such as extended-spectrum of beta-lactamases (ESBLs), carbapenem resistant or vancomycin resistant enterococci from the gastronintestinal tract of colonized patients. There have been requests from clinicians to utlize FMT for eradication of ARO in rectally colonized patients admitted to an acute care facility in order to facilitate their discharge to a longterm care facility as they were otherwise eligible to be transferred.

## **Study Objectives and Outcome Measures**

The objective of this study is to assess the efficacy of FMTs via enema for 1) symptom improvement in individuals with a formal diagnosis of dysbiosis due to active inflammatory bowel disease (CD, UC), microscopic colitis or irritable bowel syndrome; 2) clearance of antimicrobial resistant organism from the gastronintestinal tract.

### **Primary Outcome Measurements:**

For the participants with chronic GI dysbiosis, the efficacy of FMT treatment will be based on improvement in participant's symptom score from baseline (pre-transplant) to intervention (post-transplant) 4 weeks, 12 weeks and 1 year following FMT. For participants with ARO colonization, determination of clearance of ARO based on stool culture for ARO at baseline, day 7, day 30 and 3 months following last FMT.

### **Secondary Outcome Measurements for participants with IBD, MC or IBS:**

1. Evaluate efficacy and safety of FMT in patients with chronic gastronintestinal dysbiosis and antimicrobial resistant organism in the gut

2. Evaluate the Ulcerative Colitis Disease Activity Index from baseline and following each FMT using partial-MAYO score.
3. Evaluate Crohn's Diseases Activity Index (CDAI) change from baseline 4 weeks, 12 weeks and 1 year post-FMT.
4. Evaluate Microscopic colitis response to FMT using physician's global assessment and number of unformed bowel movements per 24 hours
5. Evaluate Irritable Bowel Syndrome Severity Scoring System (IBS-SSS) grade assessment change from baseline, 4 weeks, 12 weeks and 1 year post-FMT.

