### **Crohn's Disease**

CDAI is a validated instrument used in adults with active Crohn's disease. The index consists of eight factors, 2 of which are subjective: stool habits; pain; general well being; features of extra intestinal disease; use of opiates for diarrhea; abdominal mass; hematocrit (hct); and percentage of body weight below standard. Scores range from 0 to ~ 600: > 450 is severe disease; 220 – 450 moderately active disease; 150 – 219 mildly active disease. Clinical remission is defined as a CDAI score <150, clinical response is either a CDAI score <150 or a CDAI reduction of ≥100 from baseline.

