### **Irritable Bowel Syndrome**

The Irritable Bowel Syndrome Symptom Severity Scale (IBS-SSS) is a validated instrument with a scoring system which produces a meaningful value that is both reproducible and sensitive to change. The instrument contains five questions across the following domains: pain; distension; bowel score and quality of life. Each question can generate a maximum score of 100 using prompted visual analogue scales; the maximum achievable score is 500. IBS-SSS is mild for scores 75 – 175; moderate 176 – 300 and severe if > 300.

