### **Proposed sample size and the justification for the assumptions**

Fifty participants will be recruited for the chronic GI dysbiosis component of the study based on the 5% response in placebo group and 24% in FMT arm with significance level 5% and power of 80% in the FMT trial of ulcerative colitis. For the ARO participants, the sample size will be 20 as this will be a pilot project to determine the feasibility of further study.

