### **The proposed type of statistical analyses**

The clinical response rate will be determined using standard binary outcome protocols. Also, logistic regression and survival analysis methods will be performed. The primary endpoints of clinical response, and treatment failure will be analyzed by logistical regression.

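### The secondary IBS outcome is change in IBS-SSS grade, not score: it loses precision and does not match the score-based primary outcome or the UC and CD measures

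*Combined protocol and SAP*

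**What the plan says.** All references are to the combined protocol and SAP.

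- **Secondary Outcome Measurements, item 5.** The IBS outcome is "IBS-SSS) grade assessment change from baseline, 4 weeks, 12 weeks and 1 year post-FMT". Grade change is not defined further.
- **Irritable Bowel Syndrome.** The bands are given as "IBS-SSS is mild for scores 75 – 175; moderate 176 – 300 and severe if > 300". On the range of the scale: "Each question can generate a maximum score of 100 using prompted visual analogue scales; the maximum achievable score is 500". The section describes the instrument as responsive to change. It does not say how change will be measured, and it gives no response rule on either score or grade.
- **Primary Outcome Measurements.** For all participants with chronic GI dysbiosis, efficacy rests on "improvement in participant's symptom score from baseline (pre-transplant) to intervention (post-transplant) 4 weeks, 12 weeks and 1 year following FMT". No instrument and no size of improvement are named.
- **Other scored conditions.** The Ulcerative Colitis section uses change in the partial Mayo score. Item 3 of the secondary list uses change in the CDAI, and the Crohn's Disease section adds a response rule: "clinical response is either a CDAI score <150 or a CDAI reduction of ≥100 from baseline".

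Item 5 is therefore the only place that says how a change in IBS-SSS is to be assessed. IBS is also the only condition with a numerical index whose listed outcome is a grade.

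**The concern.** Reducing a 500-point scale to three wide bands discards most of the information in it. Two participants with the same fall can be recorded differently only because one started nearer a cut-off. The result then reflects the baseline distribution as well as the benefit, and the secondary IBS measure is less precise than the score from which the grade is derived.

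There is also a question of consistency. The primary outcome names no instrument, so it depends on the condition-specific items for its content. For UC and CD those items supply a score change. For IBS the item supplies a grade, and the plan does not say whether the primary symptom score for IBS is the IBS-SSS total. The trial is open-label, so the choice between score and grade should not be left until the data have been seen.

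Finally, the named bands start at 75. A participant who falls below 75 has done better than mild, but the plan gives no grade to record.

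**Working it through.** The plan states no figure on this point to reproduce, apart from the maximum: five questions at 100 each give 5 × 100 = 500, which agrees.

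**Inputs** (Irritable Bowel Syndrome section): mild 75–175, moderate 176–300, severe above 300, maximum 500. Whole-number scores are assumed.

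**Step 1. Smallest fall that changes grade.** Adjacent scores on either side of a cut-off differ by 1:

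- 301 to 300: severe to moderate
- 176 to 175: moderate to mild
- 75 to 74: mild to a range with no name

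**Step 2. Largest fall that leaves the grade unchanged.** This is the top of the band minus the bottom:

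| Grade | Band | Largest unseen fall |
|---|---|---|
| Severe | 301–500 | 500 − 301 = 199 |
| Moderate | 176–300 | 300 − 176 = 124 |
| Mild | 75–175 | 175 − 75 = 100 |

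If totals are not whole numbers, the severe figure becomes anything under 200. Listing every baseline and follow-up pair from 0 to 500 gives the same values.

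**Step 3. Illustration: how often a uniform fall changes grade.** The documents give no IBS baseline distribution, and the inclusion criteria set no minimum IBS-SSS. Two even spreads are therefore assumed.

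*Baselines even over 176–500* (500 − 176 + 1 = 325 scores). A fall of d points, with d up to 125, takes d baselines across 176/175 and another d across 301/300, so the share is 2d/325:

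- d = 10: 20/325 = 6%
- d = 50: 100/325 = 31%
- d = 100: 200/325 = 62%

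*Baselines even over 301–500* (200 scores). Only the upper cut-off matters for the first change of grade, so the share is d/200:

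- d = 50: 50/200 = 25%
- d = 100: 100/200 = 50%

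Under the first spread, half of participants change grade when 2d/325 = 0.5, that is d = 325/4, or about 81 points. Under the second, the half-way point is d = 100.

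In each line every participant has the same fall. The split between change and no change comes only from where the baseline lies. Steps 1 and 2 do not depend on the assumed spreads; Step 3 does.

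**The case against.** The strongest reply is that a score outcome already exists and is primary. IBS belongs to the chronic GI dysbiosis group, and IBS-SSS is the only IBS score in the documents. A fall from 500 to 301 can therefore be captured by the primary outcome. A grade-based secondary outcome beside a score-based primary is not a contradiction. All of this stands, and it limits the point to the secondary measure. It does not remove the point, because the primary outcome names no instrument and item 5 is the only text on how IBS-SSS change is assessed.

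A reader might infer that the plan counts a 1-point fall across a cut-off as improvement and a 199-point fall within the severe band as none. The documents do not support that. Nowhere do they make a grade shift a response, and grade change is undefined. The wording may even be loose for the assessed score, given that the parallel CDAI item refers simply to change.

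A reader might also infer that most real improvements would be missed. That does not follow either. Under the wider spread it holds only for falls below about 81 points, and a 100-point fall changes grade in 62%. The documents do not say what size of fall is a real improvement, nor how many of the 50 dysbiosis participants will have IBS.

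The missing label below 75 is minor. Leaving the mild band can be observed, but the category should still be named.

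Lastly, a change score does not supply a binary IBS response, although the statistical section states: "The primary endpoints of clinical response, and treatment failure will be analyzed by logistical regression". That is correct. It is a separate gap that the fix below does not close.

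**Conclusion.** The point holds as a matter of precision and consistency in the secondary IBS outcome. With the plan's own bands, grade can change on a 1-point fall and stay the same on falls of up to 199, 124 or 100 points in the severe, moderate and mild bands. Scores below 75 have no named grade. These figures assume only whole-number scores.

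The percentages are illustrations and depend on the assumed baselines. A 50-point fall changes grade in 31% (even over 176–500) or 25% (even over 301–500), and a 100-point fall in 62% or 50%.

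It would go too far to say that the IBS evaluation as a whole rests on grade, since the primary score outcome still covers IBS. The change is worth making because it costs almost nothing and replaces the stated measure with a more precise one.

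**What to change.** In item 5 of the secondary outcomes, replace grade change with: *change from baseline in IBS-SSS total score (0–500) at 4 weeks, 12 weeks and 1 year*. State in the same place that this total is the symptom score meant in the primary outcome for participants with IBS. Keep a grade shift table as description only, with a category for scores below 75.

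The cost is one line of protocol wording. A grade can be derived only from the total score, so the data are already collected and no visit or procedure is added.

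If the logistic regression of clinical response is to include IBS participants, a response rule for IBS must also be prespecified. The documents give no threshold, and none is proposed here.

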### **Ulcerative Colitis**

The efficacy of FMT for UC will be determined based on changes to partial-MAYO score from baseline and at weeks 4, 12 and year 1, following the treatment. Partial-MAYO is a validated scoring system to determine the activity of UC. It uses the three non-invasive components of the full Mayo Score (stool frequency, rectal bleeding and Physician's global assessment) as perceived by the patient, to score ulcerative colitis patient's disease severity score. The index considers these three clinical parameters, each of which is assigned a score from 0 to 3 according to the clinical evaluation, with a total possible score of 9. Higher the score, more severe the disease; score of 0 to 1 is considered in remission; 2 – 4 mild; 5 – 7; moderate; > 7 severe colitis.

### **Crohn's Disease**

CDAI is a validated instrument used in adults with active Crohn's disease. The index consists of eight factors, 2 of which are subjective: stool habits; pain; general well being; features of extra intestinal disease; use of opiates for diarrhea; abdominal mass; hematocrit (hct); and percentage of body weight below standard. Scores range from 0 to ~ 600: > 450 is severe disease; 220 – 450 moderately active disease; 150 – 219 mildly active disease. Clinical remission is defined as a CDAI score <150, clinical response is either a CDAI score <150 or a CDAI reduction of ≥100 from baseline.

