## GI Dysbiosis Participants

Following informed consent and pre-transplant, enrolled participants will have their blood collected for Hepatitis BsAg, Hepatitis C Ab, HIV, Syphilis serologies unless these serologies were performed within 3 months of enrollment. Blood is collected for these pathogens to determine their serostatus at the time of study enrollment and prior to receiving FMT.

All participants will be assessed at day 1 by the physician-investigator. A medical history and physical examination will be performed. In addition, optional blood and stool samples may be collected from IBD/IBS participants who consented for these samples prior to the FMT and at weeks 4, 12 and 6 months from FMT.

The participants will receive lyophilized FMT (LYO-FMT) or frozen FMT enemas using stool collected from healthy, screened donor(s). Participants will receive FMT treatment via retention enema(s) twice weekly for 4 weeks. If there is symptom improvement after 4 weeks of treatment, then the participants will receive FMT treatment once weekly for 4 additional weeks. If the participant does not experience symptom improvement after the initial 4 weeks of treatment, the physician-investigator will discuss options with the participant and a mutual decision will be reached to pursue an additional 4 weeks of FMT treatment or withdraw from the study and pursue usual care. When continued improvement is seen then the participants will receive FMT maintenance; the frequency of FMT treatment is participant dependent and is at the discretion of the physician-investigator and is based upon clinical exam and symptomatic improvement. If no improvement is seen after the 8th FMT, then the participant will be withdrawn from the study and s/he reverts to usual care for his/her condition. Participants can opt to receive maintenance FMT in the clinic or be trained by study staff for home administration.

At the time of each study visit and follow up, participants will be assessed for clinical response, including bowel movements and adverse reactions. Any participant who reports worsening symptoms or AE/SAE will return to the clinic for assessment by the physician investigator. At that time, the participant will undergo a physical exam. Additional tests may be ordered (i.e. blood work) at the discretion of the treating physician investigator.

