### **Inclusion/exclusion criteria for patients and donors**

#### **Participant inclusion criteria**

- Age 18 years or older.
- Able to provide informed consent.
- Willing and able to comply with all the required study procedures.
- Must have at least one of the following conditions
  - Underlying inflammatory bowel disease (ulcerative colitis, Crohn's disease), or microscopic colitis diagnosed by a gastroenterologist
  - Irritable bowel syndrome as defined by Rome IV diagnostic criteria\*:
    - Recurrent abdominal pain or discomfort\*\* at least 3 days/month in last 3 months associated with two or more of the following:
      - Improvement with defecation
      - Onset associated with a change in frequency of stool
      - Onset associated with a change in form (appearance) of stool
- \* Criterion fulfilled for the last 3 months with symptom onset at least 6 months prior to diagnosis
- \*\* “Discomfort” means an uncomfortable sensation not described as pain.
- Chronic severe constipation/dysbiosis as diagnosed by a gastroenterologist
- Colonized with ARO based on positive rectal cultures for same organism on 2 separate occasions (each culture 1 month apart) and must have a positive culture within 14 days of enrollment.

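### The CDAI-below-150 limb of Crohn's clinical response carries no baseline condition and entry sets no minimum CDAI, so a participant already below 150 can count as a responder without improving

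*Combined protocol and SAP*

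**What the plan says.** All references are to the combined protocol and SAP.

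- **Response rule.** The section Crohn's Disease states that "clinical response is either a CDAI score <150 or a CDAI reduction of ≥100 from baseline". It defines remission as a score under 150, and its lowest active band is 150 to 219. It introduces the index with the words "CDAI is a validated instrument used in adults with active Crohn's disease".
- **Target population.** Study Objectives and Outcome Measures speaks of a "formal diagnosis of dysbiosis due to active inflammatory bowel disease (CD, UC), microscopic colitis or irritable bowel syndrome".
- **Entry.** Participant inclusion criteria asks for "Underlying inflammatory bowel disease", diagnosed by a gastroenterologist. Participant exclusion criteria does not exclude Crohn's disease in remission. Study Population requires a formal dysbiosis diagnosis, and Recruitment leaves the final eligibility decision to the principal investigator. None of these sets a CDAI or other activity threshold.
- **Primary outcome.** Primary Outcome Measurements bases efficacy in the dysbiosis group on change ("improvement in participant's symptom score from baseline (pre-transplant) to intervention (post-transplant") at 4 weeks, 12 weeks and 1 year. The secondary list adds "Evaluate Crohn's Diseases Activity Index (CDAI) change from baseline".
- **Analysis.** The proposed type of statistical analyses says: "The primary endpoints of clinical response, and treatment failure will be analyzed by logistical regression". It does not point to the Crohn's Disease section.
- **Design.** The study is open-label, and no control arm is described.

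**The concern.** A response definition should separate participants whose disease got better from those whose disease did not. The below-150 limb does this only for someone who starts at 150 or higher, because that person must fall to meet it. For someone who starts below 150, the limb is met by standing still, or by any rise that stops short of 150.

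The entry wording does not rule such participants out. If some are enrolled and the Crohn's definition is used for the clinical-response endpoint, their stability would be reported as response to FMT. With no control arm, no comparison group contains the same kind of participant to offset them, so each one adds directly to the reported rate. That rate would then be read against an objective that concerns active disease.

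**Working it through.** The documents give no figure on this point to reproduce: no number of Crohn's participants, no baseline CDAI distribution and no Crohn's response rate. The sample size of 50 plays no part in the argument. The check is therefore a logical test of the rule, followed by an illustration on stated assumptions.

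**Step 1. Apply the written rule to example scores.** Response means post-FMT CDAI < 150, or baseline minus post ≥ 100.

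| Baseline → post | Change | Response as written | Lower than baseline? | Response if baseline ≥ 150 is required |
|---|---|---|---|---|
| 140 → 145 | +5 | yes | no | no |
| 120 → 120 | 0 | yes | no | no |
| 90 → 149 | +59 | yes | no | no |
| 151 → 149 | −2 | yes | yes, barely | yes |
| 300 → 200 | −100 | yes (second limb) | yes | yes |

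The first three rows are responses under the Crohn's Disease section but not improvements under Primary Outcome Measurements.

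**Step 2. Does the second limb help below 150?** No. From a baseline under 150, a fall of 100 would end below 50, so the first limb is already met. From a baseline under 100, a fall of 100 is impossible because the scale starts at 0. For anyone entering below 150, response therefore means only being below 150 afterwards.

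**Step 3. Illustrate the size.** Let f be the share of Crohn's participants entering below 150, s the share of those still below 150 at assessment, and p the response rate among those entering at 150 or more.

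- Reported rate = (1 − f) × p + f × s
- Excess over p = f × (s − p)

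Inputs: p = 24%, the FMT-arm figure from the ulcerative colitis trial used in the sample-size section, borrowed here for Crohn's disease. The values of f and s are pure assumptions.

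- f = 0: excess 0.
- f = 10%, s = 70%: 0.10 × (0.70 − 0.24) = 0.046, so 24% becomes 28.6%.
- f = 10%, s = 90%: 0.10 × (0.90 − 0.24) = 0.066, so 24% becomes 30.6%.
- f = 30%, s = 70% to 90%: 0.30 × 0.46 = 0.138 to 0.30 × 0.66 = 0.198.
- If all stay below 150 (s = 100%): 0.10 × 0.76 = 0.076 at f = 10%, and 0.30 × 0.76 = 0.228 at f = 30%.

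In people, at f = 10% and s = 70% to 90%: with an assumed 10 Crohn's participants, 10 × 0.046 to 10 × 0.066 = 0.5 to 0.7 extra responders; with an assumed 20, 0.9 to 1.3. The result follows the chosen inputs closely, so these figures show scale only.

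**The case against.** The strongest reply is that the protocol plainly means active disease. The objective says so, the index is introduced as one for active Crohn's disease, its lowest active band starts at 150, and dysbiosis is defined in the background section through symptoms. For that population a score under 150 always requires a fall. This stands as evidence of intent, and it makes a low f plausible. It does not close the gap: none of these statements is an entry criterion or is tied to a CDAI value. Symptoms do not guarantee a score of 150, since the index also draws on items such as hematocrit, abdominal mass and body weight.

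Second, the stated primary and secondary outcomes are changes from baseline, under which 140 to 145 is no success. That is correct, and the harm arises only if the clinical-response endpoint uses the Crohn's rule. The link is an inference, though a natural one, because no other Crohn's response definition is given.

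Third, the protocol says "If no improvement is seen after the 8th FMT, then the participant will be withdrawn from the study", which may remove some stable low scorers before the later assessments. That could reduce the effect at 12 weeks and 1 year. It does not say how such a participant is classified in the analysis; the coding of withdrawals and treatment failure is a separate point.

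A reader might also infer more than the text supports:

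- *That participants in remission will be enrolled, or that the response rate is inflated by a known amount.* Nothing in the documents shows either.
- *That the response rate across all 50 dysbiosis participants is biased.* No responder rule across the four conditions is defined, so there is no such rate to correct.
- *That ulcerative colitis, IBS and microscopic colitis share the fault.* No response cut-off is stated for them.
- *That baseline is ignored altogether.* It is used for every change score; only the below-150 limb lacks it.

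**Conclusion.** The point holds as a defect in a written rule. The below-150 limb has no baseline condition, no entry criterion supplies one, and the resulting classification contradicts the improvement-based primary outcome. This follows from the text without any assumption.

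Its effect on results is unknown. It is confined to the Crohn's subgroup, is zero if nobody enters below 150, and reaches a primary endpoint only on the inference that clinical response in the analysis section means the Crohn's definition. The illustration of about 5 to 7 percentage points rests on f = 10%, s = 70% to 90% and a 24% rate borrowed from ulcerative colitis. The correction is worth making because it is cheap and, with no control arm, no later comparison would reveal the error.

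**What to change.** 1. In the analysis, count Crohn's clinical response only among participants with baseline CDAI of 150 or more, which is the protocol's own cut-off. Report those below 150 at baseline separately as maintained remission. Keep all treated participants in the safety set.
2. Reconcile Study Objectives and Outcome Measures (*active*) with Participant inclusion criteria (*underlying*).
3. Reconcile Primary Outcome Measurements, Crohn's Disease and The proposed type of statistical analyses by stating which Crohn's definition is primary.

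**Cost.** Item 1 changes analysis wording only and uses a baseline score the plan already needs. The Crohn's efficacy denominator may shrink and its interval widen. For scale, if 30% of an assumed 20 Crohn's participants entered below 150, the denominator would fall from 20 to 14. The approximate 95% half-width around 24%, 1.96 × √(0.24 × 0.76 / n), would go from 18.7 to 22.4 percentage points. The normal approximation is rough at these numbers, so an exact interval should be used in the report.

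**Limit.** A trivial crossing such as 151 to 149 still counts as response. Reporting the CDAI change alongside, as already planned, lets a reader see such cases.
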